## Study protocol

This observational study evaluated the diagnostic and treatment-planning performance of three large language models (LLMs)—ChatGPT-4o, Claude 3.7 Sonnet, and Gemini Advanced—using real clinical cases collected from 120 patients who presented to an endodontic clinic. For each patient, a standardized case file was prepared that included demographic information, detailed medical and dental history, clinical findings (pain characteristics, percussion/palpation sensitivity, vitality testing, periodontal status, sinus tract presence, discoloration), and a periapical radiograph. All information was anonymized and presented in an identical, fixed order to all models.

Each LLM received the same single prompt (“Determine the diagnosis and propose the appropriate treatment plan”) and the same case structure. Radiographs were uploaded as original-resolution JPEG files through each platform’s native multimodal interface. Text was entered first, followed by the image upload. ChatGPT-4o, Gemini Advanced, and Claude 3.7 were all used in their default multimodal configurations with no web-browsing, plug-ins, external retrieval tools, OCR, or fine-tuning enabled. “Search with Gemini” was manually disabled.

Each case was submitted to the LLMs using newly created accounts, accessed via Google Chrome on a desktop computer. All questions were delivered within a 24-hour window and in the same predetermined order. No pre-testing, prompt engineering, or clarifying follow-up messages were allowed. If a model requested additional information, no further input was given. Each model generated only one response per case, reflecting real-world first-response performance.

To avoid contextual contamination, each case was entered in a separate chat session with cleared conversation history. All outputs were recorded verbatim and saved in Word format. A panel of

three independent endodontic specialists established the gold-standard diagnoses and treatment plans for all cases. Disagreements were resolved by consensus. AI responses were coded as “1” (consistent with gold standard) or “0” (inconsistent).

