Evaluating ChatGPT-4o, Gemini and Claude 3.7 in Endodontic Diagnostics:

A Prospective Clinical Study

NCT number: not applicable

Ethical Approval: Date: 26.06.2025, Protocol No: 2025-07-02/38

Record Release Date/Time: November 24, 2025 14:03

Last Updated: December 8, 2025

Statistical analysis

Data were entered into Excel and analyzed using SPSS (v27). Descriptive statistics were reported, and categorical comparisons were performed using Pearson chi-square or Fisher's Exact tests where appropriate, with a significance threshold of $p < 0.05$.

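### The planned Pearson and Fisher tests treat the three models as independent samples, but all three answer the same 120 cases; if their results are positively correlated within cases, the tests are miscalibrated and lose power.

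*SAP*

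**What the plan says.** The Statistical analysis section of the SAP gives one inferential rule: "categorical comparisons were performed using Pearson chi-square or Fisher's Exact tests where appropriate", "with a significance threshold of $p < 0.05". It names no other test, so any comparison of the models falls under this rule. It does not say which categories are compared, or whether the three models enter one 3x2 table, pairwise 2x2 tables, or both.

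The Study protocol section of the protocol fixes the data structure. The study works by "using real clinical cases collected from 120 patients who presented to an endodontic clinic". On the case material it says: "All information was anonymized and presented in an identical, fixed order to all models". It adds: "Each model generated only one response per case". Each answer gets a binary code for agreement with a specialist panel's reference. The panel of "three independent endodontic specialists established the gold-standard diagnoses and treatment plans for all cases". The protocol does not say whether diagnosis and treatment plan are coded separately.

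**The concern.** Each case contributes three codes, one per model. A case that is easy or hard for one model may well be so for the others, so the codes can be correlated within cases. Pearson and Fisher tests take the variance of a difference between two models as if 240 separate patients had been used. If the correlation is positive, the true variance of that difference is smaller, and the test statistic is divided by too large a quantity. The stated 5% is then not the real error rate, and real differences between models are missed more often than necessary. In a study whose purpose is to compare three named models, a non-significant result could then be read as similar performance when the test was simply insensitive.

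A second gap affects the remedy. Because the SAP does not define the set of model comparisons, replacing the unpaired test with a paired one, pair by pair, would open a multiplicity problem unless a gate is added.

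**Working it through.** **Inputs.** From the documents: 3 models, 120 shared cases, one binary code per model and case, threshold 0.05. Assumed, because the documents give neither: accuracy, and the within-case correlation phi between any two models (taken as equal for all pairs unless stated). The plan gives no power or error figure to reproduce.

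**Why pairing matters.** Let x_j be the number of correct answers for model j, x̄ their mean, p the common accuracy and p̄ its estimate. Let t_i be the number of models correct on case i.

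- Pearson, 3x2: X² = Σ(x_j − x̄)² / [120 p̄(1 − p̄)].
- Cochran's Q: Q = 6 Σ(x_j − x̄)² / Σ t_i(3 − t_i).
- The expected value of t_i(3 − t_i) is 6p(1 − p)(1 − phi), so X² ≈ (1 − phi)Q.

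Under equal accuracy Q is approximately chi-square on 2 df, with critical value 5.991. The true level of the Pearson test is therefore about exp(−5.991 / [2(1 − phi)]) = 0.05^(1/(1 − phi)):

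- phi 0: 0.05^1 = 5.0%
- phi 0.14: 0.05^1.163 = 3.1%
- phi 0.27: 0.05^1.370 = 1.7%
- phi 0.47: 0.05^1.887 = 0.4%

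**Simulation, no true difference.** 20,000 data sets per setting, 120 cases, accuracy 0.75 for all models, correlated latent normals (correlation 0 / 0.25 / 0.45 / 0.70) cut to 0/1. The simulation error at 5% is about √(0.05 × 0.95 / 20,000) = 0.15 points.

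| Chance of a false claim, one outcome | phi 0 | 0.14 | 0.27 | 0.47 |
|---|---|---|---|---|
| One 3x2 Pearson test | 5.1% | 3.1% | 1.8% | 0.4% |
| Cochran's Q | 5.0% | 5.2% | 5.3% | 4.8% |
| Any of three pairwise Pearson tests | 12.6% | 8.8% | 6.0% | 2.0% |
| Any of three ungated asymptotic McNemar tests | 12.4% | 12.2% | 12.5% | 13.1% |

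The first row agrees with the formula. For the third row, the chance that the range of three standard normals exceeds 1.96√2 / √(1 − phi) is 12.2 / 8.7 / 5.7 / 1.9%, which also agrees.

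**Simulation, one model worse.** Assumed accuracies 0.80/0.80/0.65.

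| Chance of detecting a difference | phi 0 | 0.13 | 0.26 | 0.46 |
|---|---|---|---|---|
| One 3x2 Pearson test | 79% | 80% | 81% | 83% |
| Q, then McNemar if Q is significant | 79% | 85% | 90% | 97% |
| Ungated pairwise Pearson tests | 88% | 89% | 90% | 92% |

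**Why the gate suffices with three models.** If any two of the three pairwise equalities hold, all three models are equal, and Q at 0.05 covers that case. If only one equality holds, only one McNemar test can give a false claim, and it is run at 0.05. With one model truly different, the simulated false-claim rate of the gated procedure was 4.1-5.6%. If one pair of models agrees much more than the others, the rate with all models equal was 5.1-5.8%.

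**The case against.** The strongest reply is that the planned test is safe. Read as one 3x2 table, it never exceeds about 5% under zero or positive correlation, and at phi 0 it loses nothing. The accuracy estimates themselves are unaffected by the choice of test. The study is described as observational and claims no confirmatory error rate.

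Most of this stands. There is no bias in the estimates and no inflation under the single-table reading, and the size of the loss depends on a correlation that the documents do not give. What does not stand is that the test suits the design. Its assumption is contradicted by the protocol, the loss is large at the upper end of the assumed range, and a 3x2 test cannot say which model differs. An observational or exploratory label does not turn matched codes into independent ones.

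A reader might infer something stronger: that the plan carries a 12% chance of a false difference between models. The documents do not support this. They never state pairwise tests, and the absence of a gate or adjustment is only silence. Even with pairwise Pearson tests, about 12% arises only when results are uncorrelated within cases; it is about 2% at phi 0.47. A combined error rate over diagnosis and treatment planning cannot be derived either, because separate scoring is not stated.

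**Conclusion.** The test named in the SAP is wrong for the design, whether the models are compared in one table or pairwise. This follows from the two documents and needs no assumption. Its size does: with equal positive correlation up to phi of about 0.47, the level of the 3x2 test falls as low as 0.4%, and at 0.80/0.80/0.65 power is up to 97 − 83 = 14 points below the paired procedure. At phi 0 there is no loss against the 3x2 test. Negative correlation would push the level above 5%, but that was not simulated.

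Multiplicity is a conditional note, not the main point. It matters chiefly because correcting the pairing with three ungated McNemar tests would give about 12-13% per outcome at every correlation tried.

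**What to change.** For each outcome, replace the Pearson or Fisher comparison of models with Cochran's Q at 0.05 on the 120 shared cases. Run the three McNemar tests at 0.05 only if Q is significant, and name the form used (the figures here are for the asymptotic one). Say whether diagnosis and treatment plan are scored separately, and state that the 5% applies per outcome: with two independent outcomes the combined rate would be 1 − 0.95² = 9.75%. Because the SAP is written in the past tense, label the rule as specified after data collection.

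The cost is a short paragraph and a rerun on the existing case-level codes; no new data are needed. A pairwise p just under 0.05 is not claimed when Q is not significant. Against ungated pairwise Pearson tests this loses power at low correlation (about 79% against 88% at phi 0) and gains at high correlation (97% against 92% at phi 0.46).

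The gate is approximate, at about 5-6%, if one pair of models agrees much more than the others. Holm's procedure on the three McNemar p-values avoids reliance on equal agreement; its simulated false-claim rate was 4.1-5.5% with asymptotic McNemar tests, over equal and unequal agreement.
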